12.3.5.2 Analysis of secondary endpoints

The 3 secondary endpoints evaluate the impact of 16 weeks of treatment on (i) severity and extent of AD, (ii) itch, and (iii) HRQoL. The corresponding endpoints are (i) the change from baseline to Week 16 in SCORAD, (ii) reduction (Y/N) of Worst Daily Pruritus NRS average score for the past week (hereinafter 'Worst Daily Pruritus NRS weekly average') of at least 4 from baseline to Week 16, and (iii) change from baseline to Week 16 in DLQI score. Subject-reported worst daily itch over the last week prior to baseline will be used to calculate the baseline itch (see also inclusion criterion no. 9).

Reduction of Worst Daily Pruritus NRS weekly average of at least 4 is a binary endpoint, and it will be analysed as described for the primary endpoint EASI75 using all three estimands with the modification of the ANCOVA imputation model that reduction of Worst Daily Pruritus NRS weekly average replaces EASI where preceding values are used as covariates.

The change from baseline to Week 16 in SCORAD and DLQI, respectively, are continuous endpoints and will be analysed as described below.

All analyses will be based on the full analysis set unless otherwise specified.

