Imputation of missing binary EASI75 data at Week 16 will be done using multiple imputations of the underlying 72-point EASI values within the two groups defined according to randomised treatment arm assuming that data is missing at random within each arm.

- 1. Intermittent missing values will be imputed in each group using a Markov Chain Monte Carlo method to obtain a monotone missing data pattern and 100 copies of the dataset will be generated (seed=29099725).
- 2. An analysis of covariance (ANCOVA) model is fitted to the EASI value at Week 2. The model will include effects of baseline EASI as a covariate, and region, and baseline disease severity (IGA 3 or 4) as factors. The estimated parameters, and their variances, will be used to impute missing EASI values at Week 2. 100 copies of the dataset will be generated (seed=11109925).
- 3. For each of the 100 copies of the dataset, missing EASI values at Week 4 will be imputed in the same way as for Week 2. The imputations will be based on the same ANCOVA model with effects of baseline EASI as a covariate, and region, and baseline disease severity (IGA 3 or 4) as factors together with the EASI value at Week 2 as covariate. The estimated parameters, and their variances, will be used to impute missing values at Week 4.
- 4. This stepwise procedure will then be repeated sequentially for Week 6, 8, 10, 12, 14, and 16 with the modification that only the EASI values from the preceding two visits will be included as covariates in addition to baseline EASI as a covariate, and region and baseline disease severity as factors. The missing binary EASI75 response at Week 16 will be derived from the corresponding underlying imputed EASI value.

Analysis of Week 16 response

For each of the 100 complete data sets, the difference in response rates (either the IGA 0/1 or the EASI75) between treatment groups will be analysed using the Cochran-Mantel-Haenszel test stratified by region (North America, Japan, and Europe) and baseline disease severity (IGA 3 or 4). The estimates and standard errors from the 100 analyses will be pooled to one estimated treatment difference and associated standard error using Rubin's rule to draw inference. From these pooled estimates, the 95% CI for the treatment difference will be calculated.

Sensitivity analysis for the secondary estimand

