12.3.5.1.3 Tertiary estimand: 'treatment policy'

The tertiary estimand for the primary endpoints will be:

• Treatment difference in response rate after 16 weeks between tralokinumab and placebo regardless of rescue medication and treatment discontinuation.

The tertiary estimand assesses the average difference in response rates, resulting from initiation of a treatment regimen with tralokinumab and additional rescue medication as compared to a treatment regimen with placebo and additional rescue medication.

Primary analysis for the tertiary estimand

Data retrieved at Week 16 for subjects who have permanently discontinued treatment prior to Week 16 will be included in the analysis.

Imputation of missing data at Week 16 will be done using multiple imputations within 4 groups defined according to randomised treatment arm and whether or not subjects have permanently discontinued IMP prior to Week 16. Within a given treatment arm, retrieved data from discontinued subjects will be used to impute missing data for other discontinued subjects. Similarly, the available data from not discontinued subjects will be used to impute data for such patients where the Week 16 value is missing.

For not discontinued subjects, the stepwise multiple imputations procedure will be conducted in the same way as specified for the primary analysis of the secondary estimand.

For discontinued subjects, it is expected that the number of subjects with retrieved data at Week 16 will be too small to facilitate the same imputation model as mentioned above.

Trial ID: LP0162-1325	Date: 14-Aug-2018	Version: 4.0
		Page 101 of 169

Consequently, an imputation model with only region and baseline effects (IGA as a factor and EASI as a covariate [only for EASI75]) will be applied for discontinued subjects. Some factors may have to be omitted, depending on the observed data, e.g. if retrieved subjects only come from one region or if they all have the same baseline severity.

The imputed datasets will be analysed in the same way as specified for the primary analysis of the secondary estimand.

Sensitivity analyses for the tertiary estimand

Rather than imputing Week 16 data as described in the primary analysis of the tertiary estimand, missing observations will be imputed as 'non-responders'. The assumption reflects that discontinued subjects without retrieved data at Week 16 are more likely to be non-responders than resembling discontinued subjects with retrieved data at Week 16.

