- For each of the 100 copies of the dataset, an ANCOVA model will be fitted to the SCORAD value at Week 2 in the placebo group. The model will include effects of baseline SCORAD as a covariate, and region and baseline disease severity (IGA 3 or 4) as factors. The estimated parameters, and their variances, will be used to impute missing values at Week 2 for the placebo group as well as the tralokinumab group (seed=11109925).
- 3. For each of the 100 copies of the dataset, missing values at Week 4 will be imputed in the same way as for Week 2. The imputations will be based on a similar ANCOVA model, but with SCORAD value at Week 2 included as an additional covariate. The parameters from the model will be estimated based on data from the placebo group. The estimated parameters, and their variances, will be used to impute missing values at Week 4 for both treatment groups.
- 4. This stepwise procedure will then be repeated sequentially for Week 6, 8, 10, 12, 14, and 16 with the SCORAD values from the preceding two visits included as covariates in addition to baseline SCORAD as a covariate, and region and baseline disease severity as factors.

For each of the 100 imputed dataset, the change from baseline in SCORAD at Week 16 will be analysed using an ANCOVA model with effects of treatment, region, baseline disease severity (IGA 3 or 4), and baseline SCORAD value. The estimated difference at Week 16 will be derived together with the associated standard error. The estimates and standard errors from the 100 analyses are pooled to one estimate and associated standard error using Rubin's rule to draw inference. From these pooled estimates, the 95% CI for the treatment difference will be calculated.

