# 6.6.4 Multiple imputation

For the analysis of the primary and secondary endpoints, multiple imputation will be carried out as specified in the protocol, using SAS PROC MI. For multiple imputations related to the treatment policy estimand and the hypothetical estimand sensitivity analyses, the seed 11109925 will be used. The remaining seeds are specified in the protocol.

When performing mulitiple imputation of continuous parameter values, imputed values at visits prior to Week 16 outside the relevant parameter scale shall be used as is. Values imputed at Week 16 shall be truncated to the nearest upper or lower bound on the given scale. For example, negative imputed EASI values at Week 16 will be set to 0.

For imputation of IGA values, the LIKELIHOOD=AUGMENT option will be used (1).

For imputation of IGA values, it may occur that the observed data from which the imputation model is fitted does not contain all levels of the IGA predictors necessary for the imputation. For example, the imputation model for IGA values at Week 8 will be based on observed data from the subset of subjects with observed IGA values at both Week 6 and Week 8. If only the IGA values (0,1,2,3) are observed at Week 6 in this subset of subjects, the imputation model will not be able to predict IGA values at Week 8 for a subject with an IGA value of 4 at Week 6. To avoid this situation, in this specific example IGA values of 3 and 4 at Week 6 will be combined into a single category for the purpose of the imputation. In general, if this situation

Trial ID: LP0162-1325	Date: 20-May-2019	Version: 1.0
		Page 18 of 31

arises, IGA categories will be combined into a single category at the specific visit for the purpose of the specific imputation, according to the rules in Table 1.

IGA value(s) missing in imputation model	IGA categories combined
0	(0,1)
1	(0,1)
2	(2,3)
3	(2,3)
4	(3,4)

Table 1: Adjacent IGA categories combined in case of missing predictors in observed data

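### As written, the imputation model for the itch responder endpoint keeps baseline EASI and never uses baseline itch

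*Protocol*

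**What the plan says.** Protocol 12.3.5.2 analyses a reduction of at least 4 in the Worst Daily Pruritus NRS weekly average in the same way as EASI75, under all three estimands. It states one modification of the imputation model: "reduction of Worst Daily Pruritus NRS weekly average replaces EASI where preceding values are used as covariates".

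The model being modified is in Protocol 12.3.5.1.2. Its Week 2 step reads: "The model will include effects of baseline EASI as a covariate, and region, and baseline disease severity (IGA 3 or 4) as factors". For Week 6 onwards, "only the EASI values from the preceding two visits will be included as covariates in addition to baseline EASI as a covariate". Baseline EASI and the preceding-visit values are thus separate terms.

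For the treatment-policy estimand, Protocol 12.3.5.1.3 gives discontinued subjects a reduced model with region and baseline effects, naming "EASI as a covariate [only for EASI75".

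For SCORAD, and by reference DLQI, Protocol 12.3.5.2.1 says: "The model will include effects of baseline SCORAD as a covariate, and region and baseline disease severity (IGA 3 or 4) as factors".

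SAP 6.6.4 adds nothing specific to itch. It says that "multiple imputation will be carried out as specified in the protocol" and adds a rule truncating Week 16 values to the bounds of the scale. SAP 6.6.5 limits the itch analysis to subjects with a baseline weekly average of at least 4.

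**The concern.** The NRS runs from 0 to 10, so a subject's largest possible reduction equals the baseline score. In the analysed population that ceiling ranges from 4 to 10. Take two subjects who have both improved by 2 points, one from 5 and one from 9. Their current itch is 5 − 2 = 3 and 9 − 2 = 7. To respond, the first must reach 5 − 4 = 1 or lower, the second 9 − 4 = 5 or lower. With the same EASI, region, IGA and reduction history, the model as written gives both the same imputed distribution.

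Rescue and withdrawal plausibly depend on current itch, that is, baseline minus reduction. The model conditions on the reduction but not on the baseline, so missing at random is harder to defend than it would be with baseline itch included. At stake are the arm-level response rates in the hypothetical-estimand analysis of itch. The same covariate set also carries into the copy-reference sensitivity analysis and the treatment-policy analysis. SAP 6.6.1 places itch third in the US testing sequence, so its supporting analyses are likely to be read closely.

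**Working it through.** The plan states no figure for this model, so there is none to reproduce. The check is a literal substitution, followed by simulation.

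**Step 1: substitution.** Putting the 12.3.5.2 change into the 12.3.5.1.2 model gives these predictors:

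- Week 2: baseline EASI + region + baseline IGA. No itch information.
- Week 4: the same + itch reduction at Week 2.
- Weeks 6 to 16: the same + itch reductions at the two preceding visits.

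Baseline itch is absent at every step. Treating baseline as a preceding value does not help, because the reduction at baseline is 0 for everyone. From Week 4 the preceding reductions carry some indirect information on baseline itch, so it is wholly absent only at Week 2.

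**Step 2: does truncation repair it?** No. It acts only at Week 16 and sets no subject-specific bound on a reduction. Even capping a reduction at the subject's baseline would leave it at 4 or more, since baseline is at least 4. Responder status would not change.

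**Step 3: comparison within the plan.** EASI, SCORAD and DLQI are each imputed with their own baseline. Change in Worst Daily Pruritus NRS (Protocol 12.3.5.3) follows a repeated-measures model with own baseline by visit. Only the itch responder imputation lacks it.

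**Step 4: size.** All inputs below are assumed. The reduction is the imputed variable, and region and IGA are left out of simulation 1.

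*Simulation 1.* 400,000 subjects per arm; baseline itch about N(7.5, 1.5) limited to 4–10; correlation of 0.3 with EASI; itch falls in proportion to baseline; 15% or 30% monotone missing. Drop-out is unrelated to baseline itch or more frequent at low or at high baseline. Results in % with 30% missing (error in points):

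| More drop-out at | Quantity | True | As written | With baseline itch |
|---|---|---|---|---|
| low baseline | tralokinumab | 22.8 | 23.9 (+1.1) | 23.2 (+0.4) |
| | placebo | 5.4 | 5.5 (+0.1) | 5.4 (0.0) |
| | difference | 17.38 | 18.46 (+1.08) | 17.85 (+0.47) |
| neither | tralokinumab | 22.7 | 22.9 (+0.2) | 22.8 (+0.1) |
| | placebo | 5.5 | 5.2 (−0.3) | 5.2 (−0.3) |
| | difference | 17.25 | 17.66 (+0.41) | 17.60 (+0.35) |
| high baseline | tralokinumab | 22.8 | 21.9 (−0.9) | 22.7 (−0.1) |
| | placebo | 5.4 | 4.9 (−0.5) | 5.0 (−0.4) |
| | difference | 17.40 | 17.00 (−0.40) | 17.66 (+0.26) |

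Among tralokinumab subjects missing from Week 2, across all scenarios:

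- Baseline below 5.5: imputed response 20–26% as written, 10–12% with baseline itch, true 3–5%.
- Baseline above 9: 23–26% as written, 36–40% with baseline itch, true 39–40%.

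*Simulation 2.* Baseline about 7.7 (SD 1.5), 27–47% missing, drop-out driven by current itch and mostly early. As written, arm rates are understated by 0.7–1.5 points (placebo) and 0.9–2.5 points (tralokinumab). With baseline itch the errors are 0.2–0.4 and about 0.2. The difference is off by −0.2 to −1.0 as written and +0.4 to +0.6 with baseline itch. With weaker, later drop-out, arm errors as written are below 1 point.

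*Simulation 3.* Strong, early drop-out depending on itch. Adding baseline itch moves the placebo error from −0.95 to −0.52 points and the tralokinumab error from −1.15 to +0.05. The error in the difference moves from −0.21 to +0.58.

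**The case against.** The strongest reply is that this is drafting shorthand. Every other score is imputed with its own baseline, and baseline itch is defined in the same section just before the modification. The sentence also never says that the imputed variable changes from EASI to itch, so it cannot be applied word for word. That is plausible, but a programmer directed by SAP 6.6.4 to the protocol text would still omit baseline itch as a covariate. If the score rather than the reduction were imputed, baseline itch would enter when response is derived, though still not the model, and the sizes above would differ. This is a reason to settle the wording.

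The second reply is that the estimand is a treatment difference, and the simulations show no dependable gain there. That stands: simulations 2 and 3 include cases where adding baseline itch enlarges the error in the difference. The gain is in the arm rates. For low-baseline subjects missing from Week 2 the change helps without removing the error (10–12% against a true 3–5%).

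Three stronger readings are tempting and not supported:

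- A reader might infer from the bracket in Protocol 12.3.5.1.3 that discontinued subjects have no continuous baseline covariate for itch. That bracket separates EASI75 from IGA 0/1, and 12.3.5.2 sends itch down the EASI75 branch, so baseline EASI stays. SAP 6.6.5 also says the primary treatment-policy analysis will not be estimated for itch if, as it thinks likely, discontinued subjects have no nominal Week 16 diary data.
- A reader might infer that missing at random fails for the copy-reference analysis. Protocol 12.3.5.1.2 sets that analysis up as a departure from missing at random within arm. It inherits the covariate set, but does not rest on that assumption.
- A reader might want Week 15 averages added as predictors. The documents offer no evidence on their benefit and none of the simulations tested it.

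**Conclusion.** The point holds as a minor specification flaw. On the text as written, baseline itch is not a covariate in any imputation model for the itch responder endpoint, and nothing in the SAP corrects this. Where drop-out depends on itch, arm-level response rates under the hypothetical estimand are off by roughly 0.1 to 2.5 points. The treatment difference changes by about 1 point or less, in either direction. These sizes rest on assumed baseline distributions, missingness rates and drop-out mechanisms; the documents supply none of them.

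A reader might infer that the confirmatory itch result is at risk. It is not: the testing hierarchy uses the primary analysis of the primary estimand. For itch that is the composite analysis, with rescue users and subjects missing at Week 16 counted as non-responders.

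**What to change.** In Protocol 12.3.5.2 or SAP 6.6.4, write out the itch model. State that the baseline Worst Daily Pruritus NRS weekly average replaces baseline EASI, or is added to it, in every imputation model for this endpoint: the stepwise model, its copy-reference version, and the treatment-policy model for discontinued subjects if that is run. State also whether the weekly average score or its reduction is the imputed variable.

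The cost is wording and a small programming change. Baseline itch is already collected, and every analysed subject has it because SAP 6.6.5 requires a baseline of at least 4. The SAP describes itself as prepared before unblinding, so the clarification belongs there.

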12.3.5.2.1 Primary estimand for the continuous secondary endpoints: 'hypothetical'

The primary estimand for the continuous secondary endpoints will be:

• Treatment difference in change from baseline to Week 16 in SCORAD and DLQI, respectively, if all subjects adhered to the treatment regimen in the sense that they did not discontinue IMP permanently and no rescue medication was made available before Week 16.

The primary estimand assesses the expected benefit when adhering to the treatment regimen tralokinumab with no rescue medication as compared to a treatment regimen with placebo with no rescue medication.

Primary analysis of the primary estimand (continuous secondary endpoints)

Data collected after permanent discontinuation of IMP or after initiation of rescue medication will not be included in the analysis.

The endpoints will be analysed using a repeated measurements model on the post baseline responses up to Week 16 with an unstructured covariance matrix, Kenward-Roger approximation to estimate denominator degrees of freedom, and the mean modelled as follows (shown for change from baseline in SCORAD):

Change from baseline in SCORAD

= treatment \times visit + baseline SCORAD \times visit + region + baseline IGA

This model assumes that data is missing at random within each treatment arm. The estimates will be presented with nominal p-values and 95% CI at each visit. The primary comparison between tralokinumab and placebo will be at Week 16.

Sensitivity analysis for the primary estimand (continuous secondary endpoints)

Rather than assuming that observations are missing at random within each treatment arm it is assumed that missing data from subjects who discontinue treatment/receive rescue medication in the tralokinumab arm will resemble data from subjects from the placebo arm who do not discontinue treatment/receive rescue medication. Imputation of missing data at Week 16 will be done using a pattern mixture model where missing data in the tralokinumab arm as well as the placebo arm will be imputed from the placebo arm (using a so-called copy-reference approach). The procedure for the change from baseline in SCORAD at Week 16 is described below. The same procedure will be applied for the DLQI endpoint.

1. Intermittent missing values will be imputed in each group using a Markov Chain Monte Carlo method to obtain a monotone missing data pattern and 100 copies of the dataset will be generated (seed=29099725).

- For each of the 100 copies of the dataset, an ANCOVA model will be fitted to the SCORAD value at Week 2 in the placebo group. The model will include effects of baseline SCORAD as a covariate, and region and baseline disease severity (IGA 3 or 4) as factors. The estimated parameters, and their variances, will be used to impute missing values at Week 2 for the placebo group as well as the tralokinumab group (seed=11109925).
- 3. For each of the 100 copies of the dataset, missing values at Week 4 will be imputed in the same way as for Week 2. The imputations will be based on a similar ANCOVA model, but with SCORAD value at Week 2 included as an additional covariate. The parameters from the model will be estimated based on data from the placebo group. The estimated parameters, and their variances, will be used to impute missing values at Week 4 for both treatment groups.
- 4. This stepwise procedure will then be repeated sequentially for Week 6, 8, 10, 12, 14, and 16 with the SCORAD values from the preceding two visits included as covariates in addition to baseline SCORAD as a covariate, and region and baseline disease severity as factors.

For each of the 100 imputed dataset, the change from baseline in SCORAD at Week 16 will be analysed using an ANCOVA model with effects of treatment, region, baseline disease severity (IGA 3 or 4), and baseline SCORAD value. The estimated difference at Week 16 will be derived together with the associated standard error. The estimates and standard errors from the 100 analyses are pooled to one estimate and associated standard error using Rubin's rule to draw inference. From these pooled estimates, the 95% CI for the treatment difference will be calculated.

12.3.5.2.2 Secondary estimand for the continuous secondary endpoints: 'treatment policy'

The secondary estimand for the continuous secondary endpoints will be:

• Treatment difference in change from baseline to Week 16 in SCORAD and DLQI, respectively, between tralokinumab and placebo regardless of rescue medication use and treatment discontinuation.

The secondary estimand assesses the average difference in change from baseline in SCORAD and DLQI after 16 weeks, resulting from initiation of a treatment regimen with tralokinumab and additional rescue medication as compared to a treatment regimen with placebo and additional rescue medication.

Primary analyses for the secondary estimand (continuous secondary endpoints)

Data retrieved at Week 16 for subjects who have permanently discontinued IMP prior to Week 16 will be included in the analysis. Missing Week 16 data will be imputed using multiple imputations assuming that data is missing at random within the groups used for imputation.

Imputation of missing data at Week 16 will be done using multiple imputations within 4 groups defined according to randomised treatment arm and whether or not subjects have discontinued treatment prior to Week 16. Within a given treatment arm, retrieved data from discontinued subjects will be used to impute missing data for other discontinued subjects. Similarly, the available data from not discontinued subjects will be used to impute as a subject subject of the subj

For not discontinued subjects, the stepwise multiple imputations procedure will be conducted in the same way as specified for the imputation of the underlying EASI values in the primary analysis of the secondary estimand for the binary endpoints.

For discontinued subjects, it is expected that the number of subjects with retrieved data at Week 16 will be too small to facilitate the same imputation model as mentioned just above. Consequently, an imputation model with only region and baseline effects (IGA as a factor and baseline SCORAD / DLQI as a covariate) will be applied for discontinued subjects. Some factors may have to be omitted, depending on the observed data, e.g. if retrieved subjects only come from one region or if they all have the same baseline severity.

Each of the 100 imputed datasets will be analysed and the resulting estimates and standard errors pooled as described in the sensitivity analyses for the primary estimand for the continuous secondary endpoints.

Sensitivity analyses for the secondary estimand (continuous secondary endpoints)

Rather than assuming that observations are missing at random, it is assumed that missing data from subjects in the tralokinumab arm who have/have not discontinued treatment prior to Week 16 will resemble data from subjects from the placebo arm who have/have not discontinued treatment prior to Week 16.

Imputation of missing data at Week 16 will be done using a pattern mixture model where missing data in the tralokinumab arm as well as the placebo arm will be imputed from the placebo arm (copy-reference approach). With this exemption, the multiple imputation

Trial ID: LP0162-1325	Date: 14-Aug-2018	Version: 4.0
		Page 105 of 169

procedure and analysis will be conducted in the same way as described for the primary analysis of the secondary estimand for the continuous secondary endpoints.

